**III. Research Risk**

Minimal risk means that the probability and magnitude of harm or discomfort anticipated in the research are not greater in and of themselves than those ordinarily encountered in daily life or during the performance of routine physical or psychological examinations or tests (45 CFR 46. 102). Research must present no more than minimal risk to human subjects in order to qualify for exempt or expedited review. Research must fit within one of the categories of review in order to qualify for that level of review.

Projects that propose greater than minimal risks to human subjects are considered full board protocols and they must be reviewed by the IRB at a convened meeting. The IRB meetings are held every third Wednesday of the month. Full board protocols must be submitted ten business days in advance of an IRB meeting in order to be reviewed at that month's meeting. **NOTE: Research involving prisoners is always considered a full board protocol and must be reviewed at an IRB meeting.**

A. Does the research propose greater than minimal risk to participants?  Yes  No

B. Does the research include prisoners?  Yes  No

### C. Level of Review

Please select a level of review and the appropriate category that corresponds to that level of IRB review:

- Exempt
- Expedited *Category Number: 6, 7*
- Full Board

### IV. General Study Information

Is this project a *Clinical Trial*?  Yes  No

#### A. Funding

1.  **None** (Go on to Section B)
2.  **University Funded**
3.  **External**
4.  **Federal** : List agency: NIAAA
- Sponsor Award Number (if known)  
1 K01 AA026645-02
- BC Project Number (if known)  
Not known

5. Is BC the primary awardee for the grant?  Yes  No
6. Are there subcontracts?  Yes  No

B. Participant Recruitment Numbers: This number must be the maximum number you intend to recruit. You will not be allowed to recruit more than this number without first coming back to the IRB to seek approval.

Total # of participants: 50

Do you plan to include a larger proportion of one gender group, or omit any gender groups?  Yes  No

#### C. Participant Ages (please check)

- 0-7 (parental consent and oral child assent)
- 8-11 (parental consent and child written consent)
- 12-17 (parental consent and written consent)
- 18-65
- 65+

D. Estimated Project Duration  
Start Date: 07/01/21 End Date: 08/31/23

E. Why is this Project being conducted? (please check)

- Faculty/Staff Research
- Undergraduate Coursework
- Master's Thesis
- Doctoral Dissertation
- Other:

F. Will This Study Involve Long-Term Follow-Up with participants?  Yes  No

If Yes, please describe:

There will be a 6-month post-intervention survey data collection and follow-up focus group.

#### G. Special Study Populations

- Minors (under 18 years) If including minors, also complete Research with Minors Form
- Pregnant Women/Fetuses or products of labor & delivery
- Prisoners
- Physically or mentally challenged
- Diminished capacity for consent
- Other:
- No Special Study Populations

H. Does this study involve any of the following?

- Deception or Punishment
- Use of drugs
- Covert observation
- Induction of mental and/or physical stress
- Procedures which may risk physical/mental harm to the participant
- Materials/issues commonly regarded as socially unacceptable
- Information relating to sexual attitudes, sexual orientation or practices
- Information relating to the use of alcohol, drugs or other addictive products
- Procedures that might be regarded as an invasion of privacy
- Information pertaining to illegal conduct
- Genetic information that may be linked to a participant's health status, such as genetic markers for cancer, heart disease, etc.
- Information normally recorded in a patient's medical record, and the disclosure of which could reasonably lead to social stigmatization or discrimination.
- Information pertaining to an individual's psychological well being or mental health.
- Information that if released could reasonably damage an individual's financial standing, employability, or reputation within the community.
- None of the above Procedures

Please provide details on all procedures checked above: How are they integral to the study?

The study is an substance use intervention study; thus collecting information about AOD use is important to measure effectiveness of the intervention. Additionally, anxiety and depression will be measured as they are commonly comorbid with substance misuse and are important cofounding variables to determine the effectiveness of the intervention.

## V. Research Summary:

Instructions: A research summary is a narrative that provides the IRB with important information about a study. Please provide a thoughtful response to each section using simple language and avoid technical jargon. If a specific question is not applicable to your study, please state not applicable or n/a .

### A. Introduction and Background:

#### 1. State the problem and hypothesis

There are currently no interventions aimed at preventing both alcohol and other drug (AOD) use and interpersonal violence that have been adapted for Latino adolescents. This study hypothesizes that a cultural adaptation of a validated AOD use prevention program (Keepin' it REAL) that also integrates violence prevention content will both amplify the AOD use effects of that intervention for Latino adolescents and lead to reductions in youth violence.

#### 2. Provide the scientific or scholarly reason for this study and background on the topic

Adolescent alcohol and other drug (AOD) use and interpersonal violence impose major social costs. These behaviors are also profoundly interrelated. Youth substance users are more likely to enact violence and prospective studies have shown that youth involvement in violence predicts later AOD use. It is believed that both are connected to similar underlying biosocial processes. Latino adolescents have been found to be disproportionately at risk for involvement in both substance use and violence. Latinos are also the fastest growing segment of the adolescent population, and it is predicted that the proportion of the youth population that is Latino will continue to rise in the foreseeable future. Certain Latino populations, such as Venezuelan immigrants, are rising especially quickly. There is thus a need for culturally-concordant interventions to prevent or delay initiation of both AOD use and interpersonal violence among this population.

Furthermore, the cultural adaptation literature indicates a need for more finely-grained adaptations and has encouraged focusing on more specific groups, as Latinos represent a large and diverse array of cultural backgrounds. To this end, this project will focus on Venezuelan immigrant youths. Due to the political and socioeconomic changes in Venezuela over the past several years, over 5 million Venezuelans have left their country since 2015. Cross-sectional research has found elevated psychosocial risk factors and rates of alcohol misuse among that population, indicating that they are priority population for youth prevention efforts. The initial phase of this project, which consisted of qualitative focus groups with Venezuelan migrant youth, indicated that interpersonal aggression for this population is frequently mediated through social media and online platforms, so special attention to interpersonal violence in the cyberspace will be integrated into the intervention.

## B. Specific Aims/Study Objectives:

### 1. List the purpose(s) of the study (what are you hoping to learn as a result of the study)

The purpose of this study is to conduct a pilot-test randomized controlled trial (RCT) of a youth AOD use prevention intervention that has been adapted to integrate interpersonal violence content and has been culturally adapted for a specific Latino population (Venezuelan migrant youth). The goals of the pilot test are to determine feasibility, acceptability, and preliminary effects of the intervention for future testing.

The intervention will be an adaptation of Keepin' it REAL (KiR). KiR is a 10-week intervention for early adolescents that is considered a model evidence-based AOD use prevention program by SAMHSA. It is based on communications theory and the importance of aligning cultural values with AOD outcomes. Weekly sessions focus on teaching youth communications strategies to enhance their ability to navigate situations where substance use may be present. It incorporates a student workbook, videos, and in-session discussions and exercises. We will be adapting the intervention for an online platform so that it can be delivered virtually. We will also be integrated interpersonal aggression content to expand the logic and program theory of KiR to apply to situations in which violence may arise. The goal is to both delay initiation of AOD use/aggressive behaviors and change the youth's norms around the appropriateness of AOD use and interpersonal aggression. The intervention will be delivered for the pilot study by members of the research team (PI and/or GRAs). The intervention materials will be translated into Spanish by a research team member who is a native speaker of Spanish and checked for accuracy by other members of the team. Adaptations will be made in consultation with a community advisory board that consists of Venezuelan migrants to check for cultural fit, language appropriateness, and overall concordance with the target population. All members of the research team are either fluent or proficient in Spanish.

A three-armed RCT design will be used. In addition to a control group that will receive an abbreviated, one-session workshop, one group will receive a version of the intervention that has been adapted for Venezuelan youths and the other will receive a version of the intervention that has been adapted for Venezuelan youths and includes interpersonal violence content. The purpose of this design is to determine the effectiveness of the culturally adapted KiR for the original intended outcome (reduced AOD use) and the separate effect of integrating interpersonal violence content on reducing aggressive behaviors.

## C. Materials, Methods and Analysis (quantitative and qualitative)

### 1. Describe data collection methods (Procedures) (be specific):

**Data will be collected both prior to and after the intervention. Data will be collected a pre-test prior to the intervention, which is a 10-week program consisting of weekly online sessions to provide psychoeducation and skills training regarding avoiding substance use and interpersonal aggression. The control group will participate in a one-time skills-building workshop but data will be collected at the same timepoints. Please see intervention materials included as supporting documents for more details. Data will then be collected at two time points following the intervention - immediately after and at 3 months follow-up.**

Data will be collected via self-report survey using Qualtrics. The survey will be administered via Qualtrics' email function and each participant will receive a unique link. The survey will be administered in Spanish although an English version will be available if preferred. The survey will be translated into Spanish by a research team member who is a native speaker of Spanish and checked for accuracy by other team members who are also fluent in Spanish. Cognitive interviews will be conducted with community advisory board members to determine intelligibility and cultural sensitivity of the survey. Only approved members of the research team will have access to the Qualtrics account and downloaded data will be kept in a secure database.

Focus groups will be conducted with participants after the final wave of data collection. Focus groups will focus on understanding how youth experienced the intervention program. This will be based on three core questions: What did you like/dislike about the program? What parts of the program were especially helpful/unhelpful? What would you suggest we change? Focus groups will be conducted online and recorded for transcription. **Zoom settings will be adjusted to ensure audio recordings of focus groups will be downloaded directly onto the researcher's device rather than to cloud storage.** All data collection - including surveys and focus groups - and the intervention itself will be implemented by research staff who are either qualified social workers or social work students and all of whom are either native speakers of Spanish or fluent Spanish-speakers with experience using Spanish in professional settings.

### 2. Describe the specific materials or tools that will be used to collect the data (be specific):

Survey will consist of items to gather information related to: demographics; technology access & use; cigarette, alcohol, and cannabis use; interpersonal aggression; depression & anxiety; norms regarding AOD use; and norms regarding interpersonal aggression. These items have been adapted from previous evaluation studies of KiR.

Focus groups will be conducted over Zoom and recorded for transcription. **The computer where the Zoom recordings will be temporarily stored will be password-protected.**

### 3. Describe timeline of the procedures and how long each procedure will last

**Survey data will be collected at baseline, immediately following the intervention, and at 3 months post-intervention follow-up.**

The same survey instrument will be used at all three data points. The intervention is anticipated to take place in fall 2021, with post-intervention data being collected in spring 2022. This timeline may be earlier depending on the speed of recruitment. The survey takes approx. 30 minutes to complete.

Participants will be invited to participate in a focus group after the final wave of data collection in spring 2022.

#### 4. Describe how you will analyze your data (be specific):

Exploratory descriptive analyses will be performed initially to examine variable distributions, confounding variables, and missing data. The primary analysis will be determining retention rates across all three data collection timepoints in order to establish feasibility of the intervention. The secondary analysis will examine the effect sizes between the two intervention groups and the control group will be determined regarding changes in AOD use, interpersonal violence, and norms for AOD use/interpersonal violence across the three waves of data collection.

Transcriptions will be open-coded for thematic analysis using grounded theory techniques.

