## **Statistical Analysis Plan**

We conducted a descriptive analysis of participant demographics and a basic description of baseline and follow-up outcomes. The goal of this study was to examine the feasibility and acceptability of the adapted intervention—data for this aim were based on retention and the qualitative assessment of participants and study facilitators.

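### The planned effect sizes on changes name no estimator and no adjustment for the baseline score, although every survey wave collects that score; the SAP has no between-arm effect size at all

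*Protocol*

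**What the plan says.** Protocol section V.C.4 makes retention the primary analysis: "The primary analysis will be determining retention rates across all three data collection timepoints in order to establish feasibility of the intervention". The only comparison between arms is secondary: "effect sizes between the two intervention groups and the control group will be determined regarding changes in AOD use, interpersonal violence, and norms", taken "across the three waves of data collection". The section does not say whether this means a change score, a repeated-measures model or an analysis of covariance. It names no covariate, standardising SD or interval. Confounding variables appear there only under initial descriptive work. Section IV.H names anxiety and depression as confounders, but no section plans adjustment for the baseline value of the outcome itself.

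The baseline value will be available. Section V.C.3 says "Survey data will be collected at baseline, immediately following the intervention, and at 3 months post-intervention follow-up", and adds that "The same survey instrument will be used at all three data points".

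On size, section IV.B gives "Total # of participants: 50" as a recruitment maximum, and section V.B.1 says "A three-armed RCT design will be used". Neither document gives an allocation ratio, a sample-size calculation, an SD or a pre-post correlation.

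The SAP is one short paragraph. For outcomes it offers "a basic description of baseline and follow-up outcomes", with retention and qualitative assessment for feasibility and acceptability. It has no effect size between arms, adjusted or not.

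**The concern.** An analyst who takes the V.C.4 sentence at face value would probably subtract baseline from follow-up and compare mean changes between arms. That fixes the slope on baseline at 1. When the pre-post correlation is below 1 and the SDs are similar, the best-fitting slope is r, so subtraction over-corrects. An arm that happens to start high will tend to show a larger fall for that reason alone.

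With about 16 or 17 youths per arm, chance differences at baseline can be sizeable. Section V.B.1 lists early estimates of effect, to inform later testing, among the pilot's goals. These effect sizes are therefore something the trial intends to deliver, even though they are secondary. A more precise estimator is available from data that the trial already plans to collect.

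**Working it through.** The documents state no figure for this analysis, so there is nothing to reproduce first.

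**Inputs**
- Maximum of 50 participants (Protocol IV.B) in three arms (V.B.1).
- Assumed: 1:1:1 allocation, giving arms of 17, 17 and 16. One contrast of 17 v 16 has N = 33.
- Assumed: a roughly continuous score with the same SD (set to 1) at baseline and follow-up, and no attrition.
- Not given: the pre-post correlation r, so a range is shown.

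**Formulas, per-youth variance**
- Change score: 2(1 − r).
- Baseline-adjusted: 1 − r².
- Ratio of adjusted to change score: (1 − r²) / [2(1 − r)] = (1 + r)/2.
- Small-sample cost of one covariate: 1 + 1/(N − 4) = 1 + 1/29 = 30/29 = 1.034.
- 95% half-width: 1.96 × √[variance × (1/17 + 1/16)], where √(1/17 + 1/16) = √0.1213 = 0.348.

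**Results** (adjusted figures include the covariate cost; half-widths in SD units)

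| r | Change variance | Adjusted variance | Ratio | Half-width, change | Half-width, adjusted |
|---|---|---|---|---|---|
| 0.3 | 1.40 | 0.91 × 1.034 = 0.94 | 0.67 | 0.81 | 0.66 |
| 0.5 | 1.00 | 0.75 × 1.034 = 0.78 | 0.78 | 0.68 | 0.60 |
| 0.7 | 0.60 | 0.51 × 1.034 = 0.53 | 0.88 | 0.53 | 0.50 |
| 0.9 | 0.20 | 0.19 × 1.034 = 0.20 | 0.98 | 0.31 | 0.30 |

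At r = 0.5 the saving is equivalent to 1/0.776 = 1.29, or about 29% more participants. Break-even is where (1 + r)/2 × 30/29 = 1, that is r = 58/30 − 1 = 0.93. Above that, adjustment loses, but only trivially. If 20% were lost (assumed), the half-widths at r = 0.5 would be about 0.76 and 0.67 SD.

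**Where the excess comes from**
- The chance baseline difference between two arms has a standard error of 0.348, about 0.35 SD.
- Given a baseline difference d, the change-score contrast is shifted by −(1 − r)d. For d equal to one standard error the shift is 0.24 SD at r = 0.3, 0.17 at r = 0.5, 0.10 at r = 0.7 and 0.03 at r = 0.9, always opposite in sign to d.
- Before the covariate cost, the variance excess is 2(1 − r) − (1 − r²) = (1 − r)². That is exactly the variance contributed by this shift, so imprecision and imbalance are one harm and should be counted once.

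**The case against.** The strongest objection is that the text does not commit to a change score. A reader might infer that the plan has chosen raw change from baseline over an adjusted analysis. It has not: change over three waves is also compatible with a group-by-time model. In a repeated-measures model with a common baseline mean, the difference between arms in change equals the difference at follow-up. This part of the objection stands. What the documents show is an unnamed estimator and no stated adjustment for the baseline outcome.

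A reader might also infer that youths missing one wave will be dropped. That presumes a complete-pair analysis, which is not stated. V.C.4 says that missing data will be examined, though it gives no method.

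Three further limits stand:
- Section V.C.2 lists survey topics and items but no scales or scoring. It is an assumption that norms and aggression will form roughly continuous scores. At ages 11 to 14, substance use and aggression may be mostly zero, and the formulas above do not carry over directly to such data.
- The gain depends on r and almost vanishes at 0.9.
- Intervals at this sample size are wide either way, and the documents attach no decision rule to these effect sizes.

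None of this removes the point. Neither document plans adjustment for the baseline outcome, the baseline is collected anyway, and stating the adjusted analysis is sensible under either reading of the sentence.

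**Conclusion.** The point holds as a gap in specification with a clearly better option at hand. If the secondary analysis is done as simple change scores, the baseline-adjusted contrast would have about 0.67 to 0.88 of its variance for r from 0.3 to 0.7, and 0.98 at r = 0.9. This rests on 1:1:1 allocation of the maximum 50, equal SDs, no attrition and roughly continuous scores. None of these is given in the documents.

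A reader might infer that change scores would bias the trial's results. They would not on average: over randomisation the change-score contrast is unbiased. The shift is conditional on whatever imbalance happens to occur, although in a single small trial it can be material.

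The consequence is limited to secondary estimates in a pilot. The primary retention analysis is unaffected. The absence of any between-arm effect size from the SAP is a separate and larger gap, and the same edit can close it.

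**What to change.** **In Protocol V.C.4.** For outcomes scored as roughly continuous (the norms scores, and aggression if it is scored that way), state that each intervention arm will be compared with control at each follow-up, adjusted for the baseline value of the same score, with a 95% interval. Use one repeated-measures model of the two follow-ups with baseline as a covariate, so that youths missing one follow-up still contribute. Name the SD used to standardise the effect size.

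**For sparse or binary outcomes.** Use a suitable generalised model with the baseline value as covariate.

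**In the SAP.** There is no change-score wording to replace. Add the same analysis, so that the SAP agrees with V.C.4.

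**Cost.** One degree of freedom per outcome, some wording and a little more analysis work. No new data are needed.

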### D. Research Population & Recruitment Methods:

#### Describe:

#### 1. Inclusion and Exclusion Criteria (what participant traits are needed to be included, what traits exclude participants?)

Inclusion criteria are 1) being born in Venezuela, 2) currently residing in the U.S., and 3) being between the ages of 11-14 at the time of recruitment. Participants will also need access to the internet and technology to complete the surveys and participate in the intervention. AOD use and/or engagement in interpersonal aggression will not be considered for purposes of inclusion/exclusion, unless the participant is intoxicated to the point of being unable to successfully complete a survey or participate in the intervention. Participants will also be excluded if they are otherwise cognitively unable to successfully engage in the intervention. **The GRA who is consenting the participant will determine capacity. All GRAs who will be consenting participants will be either clinical MSW students who have experience performing mental health assessments or licensed mental health professionals. The GRAs who are licensed mental health professionals will also be available to consult with the student GRAs as needed. If there are questions or concerns about capacity to consent, final determination will be made by the PI.**

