#### 2. What is the scientific or scholarly justification for the number, gender, age, or race of the population you intend to recruit?

Early adolescence is a critical developmental window. AOD use and aggression in early adolescence have been linked to higher risks for later negative psychosocial outcomes, including substance use disorders, thus making it an important life stage in which to intervene. Furthermore, the empirically-validated intervention that is being adapted (KiR) is aimed at early adolescents (specifically 7th graders), so a similar age group will be recruited to maintain treatment fidelity.

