#### 4. Recruitment procedure; including who will recruit participants and, if applicable, how any conflict of interest/coercion/undue influence will be mitigated

The research team will recruit participants in conjunction with the community partner in Florida. Specifically, our community partner will inform parents about the opportunity to participate and the research team will then communicate with parents and kids. We will then select participants in the order that they express interest, enrolling only those who have received informed consent and provide assent. Our point of contact is with parents who will be told about the study and will then have the discretion to proceed with informing their children about the possibility of participation. We will specifically instruct our community partners that participation must be voluntary and free of coercion, and we too will communicate this verbally and in our consent documents. We will communicate to our community partner that it is critical that youth have the freedom to tell partner agencies that they prefer not to participate. Please note that our community partner will NOT be consenting participants--as such, we are in a position to ensure that all youth participate without coercion. Although the our primary community partner is not a member of the research team for this project, she has completed CITI training and has previously received instruction from the PI concerning human subjects research, coercion, etc. All recruitment is via word-of-mouth. Recruited participants may also be asked to refer other potential participants.

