**2. Consider the likelihood of the benefits. Will all or some participants benefit?**

All participants are equally likely to gain benefit from participation in the various interventions, although those randomized to the full intervention may receive greater benefit. All can potentially benefit from feeling like they are contributing to an intervention to help their community.

**I. Investigator experience. Please attach a current copy of your C.V. unless a current copy is on file. Note: the IRB only needs the C.V. from the PI, not the faculty advisor.**

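### Neither document balances the three arms on age or adjusts the secondary effect sizes for it: a modest, avoidable loss of precision, not a bias

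*Protocol*

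**What the plan says.** Protocol section IV.B sets "Total # of participants: 50" as the recruitment maximum. Section V.B.1 states "A three-armed RCT design will be used", and V.D.1 requires "being between the ages of 11-14 at the time of recruitment". V.D.2 justifies the age group by noting that the parent programme "is aimed at early adolescents (specifically 7th graders), so a similar age group will be recruited to maintain treatment fidelity". On entry, V.D.4 says "We will then select participants in the order that they express interest".

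Randomisation is mentioned (V.B.1, and V.H.2, where "those randomized to the full intervention may receive greater benefit") but not described. No ratio, sequence generation, blocking, stratification or minimisation appears in either document.

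On analysis, V.C.4 says "The primary analysis will be determining retention rates across all three data collection timepoints in order to establish feasibility of the intervention". Effect sizes of the two programme arms against control come second, and they concern changes in use, violence and norms over the three surveys. V.C.4 also plans a descriptive look at confounders without naming any or saying what follows. IV.H names anxiety and depression. Age is not named as a covariate anywhere. The SAP describes demographics and baseline and follow-up outcomes, and gives feasibility and acceptability as the goal.

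**The concern.** In early adolescence, substance use and the norms around it may well depend on age, and V.B.1 makes later initiation a goal of the programme. The eligible span covers several school grades, although the parent programme was built for one. With 16 or 17 youths per arm, chance alone can leave one arm noticeably older than another. The secondary effect sizes, which V.B.1 wants as preliminary evidence for future testing, would then carry that difference, and no planned step would remove it or show it. Age is already known at screening, so controlling it costs almost nothing.

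**Working it through.** The documents give no figure for imbalance, power or precision, so there is none of theirs to reproduce.

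**Inputs.** From the protocol: at most 50 youths, three arms, ages 11-14. Assumed: 1:1:1 allocation (17/17/16) and the age distribution, because no mean or SD is given. Ages spread evenly over 11.0-14.99 have SD 4/√12 = 1.155 y. Ages spread evenly but ending at the 14th birthday have SD 3/√12 = 0.866 y. Ages clustered around the parent programme's grade are given SD 0.8 y.

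**Step 1: chance of a half-year gap.** For one pair of arms, SE = SD × √(1/17 + 1/16) = SD × 0.348, and P(gap ≥ 0.5 y) = 2 × [1 − Φ(0.5/SE)]. The any-pair column is from simulation.

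| Assumed ages | SE (y) | 0.5/SE | Given pair | Any of three pairs |
|---|---|---|---|---|
| Even, 11.0-14.99 | 0.402 | 1.24 | 21% | 43% |
| Even, ending at 14.0 | 0.302 | 1.66 | 10% | 22% |
| Clustered, SD 0.8 | 0.279 | 1.79 | 7% | 16-17% |

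For at least one programme arm against control, the comparison V.C.4 plans, evenly spread ages over 11.0-14.99 give about 35%. Fewer youths raise these chances. With 30 enrolled, the any-pair chance is about 40% to 64% over a similar set of assumed age distributions.

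**Step 2: what stratifying would do.** Permuted blocks of three within the bands 11-12 and 13-14, with ages even over 11.0-14.99, lower the any-pair chance from about 43% to about 4%, and the given-pair chance from about 21% to under 2%.

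**Step 3: what a gap does to a comparison of levels.** If the outcome rises 0.1 to 0.3 SD per year of age (assumed), a half-year gap shifts the comparison by 0.05 to 0.15 SD. The standard error of a standardised difference for 17 v 16 is √(1/17 + 1/16) ≈ 0.35 SD.

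**Step 4: what it does to a comparison of changes.** Let level = a + b × age. Over a period t every youth changes by b × t whatever the starting age, so an older arm shows the same change and the gap cancels. If instead the yearly rise b itself climbs with age at rate g per year, an age gap d leaves a difference in change of g × d × t. As an illustration, let any-use rise 4 points a year at 11 and 8 points a year at 15 (assumed), so g = 4/4 = 1. With t = 10/52 + 0.25 = 0.44 y (10 weeks plus three months, V.C.1), the residue is 1 × 0.5 × 0.44 = 0.22 points. With the six-month follow-up mentioned in IV.F, t = 0.69 y and the residue is 0.35 points. For scale, the standard error of a simple difference in proportions for 17 v 16 is √(p(1 − p)) × 0.348, or 7.6 points at p = 5% and 13.9 points at p = 20% (assumed rates).

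**Step 5: precision gained by adjusting.** If age correlates r with the outcome analysed (given baseline, if that is also in the model), the SE is multiplied by √(1 − r²). Estimating the age slope costs a factor of about √(1 + 1/45), where 45 = 50 − 3 arms − 2.

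- r = 0.3: 0.954 × 1.011 = 0.964, a gain of about 4%.
- r = 0.4: 0.917 × 1.011 = 0.927, a gain of about 7%.
- r = 0.1: 0.995 × 1.011 = 1.006, no gain.

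**The case against.** The strongest reply is that this is ordinary chance imbalance in a small feasibility pilot. Randomisation makes the comparison unbiased over repetitions, chance age gaps are already part of the sampling error, retention is the primary analysis, and the effect sizes are planned on changes. All of that stands, and it limits the point to precision and reporting. It is also fair that choosing age to stratify on, rather than sex or baseline risk, is partly a preference, and that V.C.4 does promise to examine confounders.

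The reply does not dispose of the point, for three reasons. Cancellation needs a linear age trend; where most youths start at zero use (likely, but an assumption), change is mostly new onset, and an onset rate that rises with age does not cancel. The SAP's plain description of baseline and follow-up outcomes lets a reader compare unadjusted follow-up levels across arms. And no confidence intervals are planned, so that reader would not see how wide the sampling error is.

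A reader might go further and infer that allocation is unrestricted, so that an arm of 12 or fewer would arise in about 31% of trials. That figure presumes simple randomisation. The documents state no method, and silence does not establish that one. The missing description is a separate reporting gap, unrelated to age.

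**Conclusion.** The point holds as a modest, nearly free improvement. No age balancing or age adjustment is planned, and at the full 50 a half-year gap in mean age would arise in about 7% to 21% of trials for a given pair of arms and about 16% to 43% for some pair. These figures rest on 1:1:1 allocation and on age distributions that are assumed.

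A reader might infer that arms will routinely differ enough for age to pass as a programme effect, for example by 2 to 4 points in any-use from a half-year gap at 4 to 8 points per year. The documents do not support that. Those points are a shift in level, whereas V.C.4 plans changes, in which a constant yearly rise cancels. The high frequency needs evenly spread ages and counts any of three pairs. The exposure is confined to onset or change rates that themselves vary with age, and to unadjusted follow-up levels read across arms. Even on levels, an assumed 0.05 to 0.15 SD shift is small beside a standard error of about 0.35 SD.

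**What to change.** In protocol V.C.4 and the SAP, state that each programme-versus-control effect size is estimated with the baseline value and age in years as covariates and reported with a confidence interval, and that age is tabulated by arm. This can be done even if allocation is complete.

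If allocation has not been done, state in V.B.1 or V.D.4 that it is 1:1:1 from a computer-generated list in permuted blocks within two age bands (11-12 and 13-14).

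The cost is one degree of freedom for age, a short allocation list and a few incomplete blocks, with no extra youths or data. The return is a standard error about 4% to 7% smaller if age correlates 0.3 to 0.4 with the outcome analysed, and close to nil at 0.1.
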